14.6. Secondary Analysis

CLUE Comfort and Vision scores

CLUE scores at follow-up visits will be analyzed using a MMRM model for comfort and vision respectively to compare between Test and Control lenses at 2-week follow-up. Each regression model will include the baseline score, lens type, visit, and the interaction of lens type and visit as fixed effects and investigational site as a random effect (G-side). Age and gender will also be included as fixed effects. The covariance of residual errors between different periods for the same subject will be modeled using an unstructured (UN) covariance structure. The Kenward and Roger method will be used for the calculation of the denominator degree of freedom.⁸

The null and alternative hypotheses for non-inferiority of Test lens relative to Control are as follows:

$$H_0: \Delta < -5$$
$$H_A: \Delta \geq -5$$

where Δ is the CLUE score mean difference between Test lens and Control lens (Test minus Control) at 2-week follow-up. The hypothesis will be tested via the corresponding two-sided 95% confidence interval (CI) for least squares mean (LSM) difference (Test - Control) in CLUE scores. Non-inferiority will be declared if the lower bound of the confidence interval of the mean difference between Test and Control is greater than -5.

14.7. Other Exploratory Analysis

Not applicable.

14.8. Interim Analysis

Not applicable.

Clinical Study Protocol

Johnson & Johnson Vision Care, Inc.

14.9. Procedure for Handling Missing Data and Drop-Outs

Missing or spurious values will not be imputed. The count of missing values will be included in the summary tables and listings.

Subject dropout due to reasons other than Adverse Event is expected to be the main reason of missing data in this study and is expected to be no larger than 10 percent. Prior studies don't provide the evidence that subject dropout or major protocol deviation is systematic or not-at-random. Therefore, the primary and secondary analyses based on mixed model which is robust under missing-at-random (MAR) would be sufficient for this study⁹. If the percentage of missing data for primary or secondary endpoints is greater than 15 percent, further sensitivity analyses will be conducted to confirm the validity of the missing data assumptions.

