Trial Registration	This study will be registered on ClinicalTrials.gov by the Sponsor.
Test Article(s)	
Investigational Products:
 
 • senofilcon A contact lenses made with a novel manufacturing technology (Test). • senofilcon A contact lenses made with the current manufacturing technology (Control). 
Approved Products: None

Wear and Replacement Schedules	
Wear Schedule: daily wear
 
Replacement Schedule: daily disposable

Objectives	To evaluate the clinical performance of senofilcon A contact lenses made with a new manufacturing technology as compared to senofilcon A contact lenses made with the existing manufacturing technology.
Study Endpoints	
Co-primary endpoint(s):
 
 • Monocular distance visual performance after 1- and 2-weeks of lens wear • Average daily wear time (in hour) after 1- and 2-weeks of lens wear 
Secondary endpoint(s):
 
 • Overall comfort after 2-weeks of lens wear • Overall quality of vision after 2-week of lens wear 
Additional Endpoints:
 
 • Slit lamp findings • Subject reported ocular symptoms • Lens fitting characteristics • Lens wettability • Adverse events • Reasons for discontinuation • Lens damage • MRD/GSI items

Clinical Study Protocol
Johnson & Johnson Vision Care, Inc.

Study Design	
This study is a feasibility, multi-site, randomized, double-masked, 2-arm parallel group design, 2-week dispensing study with weekly visits. Subjects will wear bilaterally either the Test or Control lenses (randomly assigned) for 2-weeks in a daily disposable modality.
 
See the flow chart at the end of the synopsis table for the schematic of the study visits and procedures of main observations (Figure 1).

Sample Size	Approximately 115 eligible subjects will be enrolled and randomized into the study to ensure that approximately 100 subjects (~50 in the Test group and ~50 in the Control group) complete as cohort.
Study Duration	There will be a 6-week enrollment window. The study will last approximately 2 weeks per subject. Therefore, the entire study will last approximately 8 weeks per site.
Anticipated Study Population	Healthy male and female adults of any race and ethnicity who meet the eligibility criteria can participate. The study will target habitual wearers of daily disposable silicone hydrogel contact lenses.

Clinical Study Protocol

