14.2. Sample Size Justification

The plan is to enroll 115 subjects with a target completion of 100 subjects with approximately 50 subjects in the Test group and approximately 50 in the Control group. This is a feasibility study, and the sample size is chosen not based on estimates from historical studies with the product characteristics. The data collected for this study will be used to design future clinical trials. Thus, power calculations were conducted under different scenarios for the primary hypotheses to provide estimates on power with 2-sided type I error of 0.05 given the parallel design and 1:1 randomization ratio for average daily wear time and LogMAR visual acuity test at a 4-meter distance under high luminance/low contrast (HLLC) and low luminance/high contrast (LLHC) conditions.

Table 7 provides a summary of power based on the hypothesis of non-inferiority for logMAR visual acuity test at a 4-meter distance under either HLLC or LLHC at 1 Week Follow-up visit with a non-inferiority margin of 0.05 logMAR. Table 8 provides a summary of power based on the hypothesis of non-inferiority for average daily wear time at 1-week follow-up visit with a non-inferiority margin of 1 hour. The power calculation based on two sample t-test is conducted using the POWER procedure in SAS 9.4.

Clinical Study Protocol

Johnson & Johnson Vision Care, Inc.

Table 7: Power Calculation for the first primary hypothesis of logMAR visual acuity for either HLLC or LLHC at 2-week follow-up with a non-inferiority margin of 0.05.

Mean Difference (Test - Control)	Type I error	Standard Deviation	Total Sample Size (n/2 per arm)	Power
-0.01	0.05	0.08	100	0.981
-0.01	0.05	0.09	100	0.952
-0.01	0.05	0.10	100	0.909
0.00	0.05	0.08	100	0.928
0.00	0.05	0.09	100	0.867
0.00	0.05	0.10	100	0.799

As shown in the Table 7, the power is 0.8 or higher to show non-inferiority of the Test relative to the Control with respect to logMAR VA test at a 4-meter distance under either HLLC or LLHC when the Test - Control ≤ 0 and the standard deviation for both Test and Control < 0.10 .

Table 8: Power Calculation for the second primary hypothesis of average daily wear time at 2-week follow-up with a non-inferiority margin of 1.

Mean Difference (Test - Control)	Type I error	Standard Deviation	Total Sample Size (n/2 per arm)	Power
-0.05	0.05	1.90	100	0.799
-0.05	0.05	1.93	100	0.788
0.00	0.05	1.90	100	0.834
0.00	0.05	1.93	100	0.823
0.05	0.05	1.90	100	0.864
0.05	0.05	1.93	100	0.855

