14.3. Analysis Populations

Safety Population:

All subjects who are administered any test article excluding subjects who drop out prior to administering any test article. At least one observation should be recorded.

Per-Protocol Population:

All subjects who successfully complete all visits and do not substantially deviate from the protocol as determined by the trial cohort review committee prior to database hard lock. Justification for the exclusion of subjects with protocol deviations from the per-protocol population set will be documented in a memo to file.

Intent-to-Treat (ITT) Population:

All randomized subjects regardless of actual treatment and subsequent withdrawal from the study or deviation from the protocol. At least one observation should be recorded.

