14.5. Primary Analysis

The co-primary endpoints for this study are the logMAR VA test at a 4-meter distance under either HLLC or LLHC and the average daily wear time at 2-week follow-up evaluated after 14 ± 4 days of lens wear. The primary analysis will be conducted on per-protocol populations.

Visual Performance

Monocular distance visual performance in logMAR scale at follow-up visits will be analyzed using a mixed model of repeated measurement (MMRM) for HLLC and LLHC respectively to compare between Test and Control lenses at 2-week follow-up. The model will include baseline logMAR, lens type, visit, and the interaction of lens type and visit as the fixed effect, and investigational site and patient as random effects. Baseline demographics such as age and gender have historically limited influence on objective visual performance; thus, in accordance with the principle of parsimony, will not be included in the model. The covariance of residual errors between two follow-up visits across periods for the same eye and subject across wearing periods will be modeled using an unstructured (UN) covariance structure.

The null and alternative hypotheses for non-inferiority of Test lens relative to Control are as follows:

$$H_0: \Delta > 0.05$$
$$H_A: \Delta \leq 0.05$$

Clinical Study Protocol

Johnson & Johnson Vision Care, Inc.

where Δ is the mean difference in logMAR between Test lens and Control lens (Test minus Control) at 2-week follow-up. Non-inferiority will be declared if the upper bound of the confidence interval of the mean difference between Test and Control is less than 0.05.

Average Daily Wearing Time

Average daily wear time will be analyzed using a similar MMRM model with fixed and random effects described in the primary analysis. Age and gender will also be included as fixed effects.

The null and alternative hypotheses for non-inferiority of Test lens relative to Control are as follows:

$$H_0: \Delta < -1$$
$$H_A: \Delta \geq -1$$

where Δ is the mean difference in average daily wearing time between Test lens and Control lens (Test minus Control) at 2-week follow-up. Non-inferiority will be declared if the lower bound of the confidence interval of the mean difference between Test and Control is greater than -1.

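### The missing-at-random argument in section 14.9 does not cover subjects removed from the completer-only primary analysis, and the 15% condition makes it unlikely that departures from that assumption would be explored

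*Combined protocol and SAP*

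**What the plan says.** Section 14.9 makes four statements about missing data:

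- No imputation: "Missing or spurious values will not be imputed".
- Dropout for reasons other than adverse events "is expected to be no larger than 10 percent".
- Analyses based on a "mixed model which is robust under missing-at-random (MAR) would be sufficient for this study".
- A conditional safeguard: "If the percentage of missing data for primary or secondary endpoints is greater than 15 percent, further sensitivity analyses will be conducted". Neither the denominator of this percentage nor a sensitivity method is given.

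Section 14.5 fixes the primary population: "The primary analysis will be conducted on per-protocol populations". Section 14.3 defines that set as "All subjects who successfully complete all visits and do not substantially deviate from the protocol". It also defines an ITT set of all randomised subjects with at least one observation, but section 14 assigns no analysis to it. Section 14.6 names no population for the secondary analysis, and section 14.7 plans no other exploratory analysis.

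On numbers, section 14.2 says "The plan is to enroll 115 subjects with a target completion of 100 subjects". The synopsis makes clear that the 115 are randomised: "Approximately 115 eligible subjects will be enrolled and randomized into the study to ensure that approximately 100 subjects".

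Section 8.2 lists a missed visit among the reasons for withdrawal. The list also includes non-compliance with the wear schedule, and unsuccessful dispensing because of poor vision, poor comfort or unacceptable fit.

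**The concern.** A mixed model for repeated measures protects against MAR dropout by using what dropouts contributed before they left. Here that would be the 1-week values of someone who stops before week 2. The per-protocol set removes such subjects entirely, so the model never sees those values. The justification in 14.9 therefore describes an analysis of all randomised subjects, whereas the one planned in 14.5 is an analysis of completers.

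The losses may also relate to outcome. Continuing past Visit 2 requires a minimum acuity in each eye (step 2.16), and vision is a co-primary domain. Insufficient daily wear is a major deviation (Table 6) and can therefore lead to exclusion from the per-protocol set. Non-compliance with wear is also a withdrawal reason, and wear time is the other co-primary endpoint. If more poor performers were lost on Test than on Control, the completer comparison would lean towards non-inferiority. The one provision that might examine this is conditional, and the plan's own figures suggest that the condition will probably not be met.

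**Working it through.** **1. Attrition implied by the plan.** Inputs: 115 randomised and 100 completing (synopsis, 14.2).

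- Implied loss: (115 − 100)/115 = 15/115 = 13.0%.
- Check: 100/(1 − 0.13) = 114.9, rounded up to 115, which reproduces the enrolment figure. The 10% in 14.9 would give 100/0.90 = 111.1, rounded up to 112.
- The 13.0% is derived; the documents do not state it. It and the stated 10% both lie below 15%.

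**2. Reaching the condition over all randomised subjects.** 17/115 = 14.8% does not exceed 15%, and 18/115 = 15.7% does, so at least 18 subjects must be missing. With X ~ Binomial(115, p):

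| True missing proportion p | P(X ≥ 18) |
|---|---|
| 10% (expectation in 14.9) | 0.037 |
| 13.04% (implied by 115 and 100) | 0.239 |
| 14% | 0.343 |
| 15% | 0.462 |

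**3. Reaching it within the per-protocol set.** With 100 completers, at least 16 values must be missing. The documents give no rate for missing items among completers, so I assume a range. P(X ≥ 16) for Binomial(100, p) is 6 × 10⁻¹⁵ at 1%, 4 × 10⁻⁵ at 5% and 0.006 at 8%. This is practically unreachable, though not impossible. Appendix E treats a remote visit as a minor deviation, so a completer without an in-clinic logMAR value could remain in the set.

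**4. How large an unexplored departure would matter.** This is an illustration. Assumptions: observed difference zero; 50 per arm; 13.04% of Test missing, with a mean worse by δ than Test completers; no differential loss in Control; interval width held at the completer value.

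- Half-width = t × SD × √(2/50) = t × SD × 0.2, on 98 degrees of freedom.
- Non-inferiority is lost when 0.1304 × δ = margin − half-width.
- SDs are from Tables 7 and 8. Section 14.5 gives no confidence level for the primary endpoints, so both candidates are shown. Section 14.6 uses a two-sided 95% interval. The power values in Tables 7 and 8 reproduce to three decimals only at one-sided 5%, which corresponds to a 90% interval.

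| Endpoint (margin) | SD | Half-width, 95% CI | δ, 95% CI | δ, 90% CI |
|---|---|---|---|---|
| logMAR (0.05) | 0.08 | 0.0318 | 0.14 | 0.18 |
| logMAR (0.05) | 0.10 | 0.0397 | 0.08 | 0.13 |
| Wear time (1 h) | 1.90 | 0.754 | 1.9 h | 2.8 h |
| Wear time (1 h) | 1.93 | 0.766 | 1.8 h | 2.8 h |

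Example: (0.05 − 0.0397)/0.1304 = 0.079 logMAR. Every tipping value lies beyond the margin itself, which matters for the design of the fix.

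**The case against.** The strongest reply is that the 15% is not tied to the per-protocol set. Section 14.9 discusses dropout and major deviations as sources of missing data, which makes most sense if those subjects are in the denominator. On a randomised base the rule can operate, and setting a contingency threshold above expected loss is a legitimate choice. The binomial figures may also be low. They count one source of loss on a fixed 115, while discontinued subjects are replaced (5.3, 8.2), several endpoints could each cross 15%, and deviation exclusions might be counted as well. At 15% true missingness the chance is 46%. The study is also labelled feasibility with exploratory hypotheses (2.3), the two lenses share material, base curve, diameter and power range (Table 1), and discontinuation reasons and missing counts will be summarised.

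Much of this stands, and it rules out three stronger readings.

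- A reader might infer that the safeguard is inoperative by definition. The base is unstated, so the documents support only that it would probably not run.
- A reader might infer that MAR would otherwise be tested. It cannot be tested from observed data; sensitivity analyses explore departures from it.
- A reader might infer that the 15% rule inflates the error rate. It does not, because a sensitivity analysis leaves the primary decision unchanged. If 13% of Test were lost with wear time 1 to 3 h below the MAR prediction and Control losses were random, one-sided error would rise from 2.5% to 5.2–17.1% (SD 1.93, 50 per arm, two-sided 95% interval). That illustrates completer-only bias under an assumed Test-only mechanism and is not an effect of the trigger.

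The reply does not repair the mismatch between the MAR argument and the completer set. Nor do descriptive summaries show how far the conclusion depends on the missing values.

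**Conclusion.** The point holds as a mismatch between justification and analysis, together with a safeguard that would probably stay unused. The mismatch follows directly from 14.3, 14.5 and 14.9 and needs no numerical assumption. The chance that sensitivity analyses run is about 4% at the loss expected in 14.9 and 24% at the loss implied by the sample size, taking 115 as the base and independent losses. It approaches an even chance only if true missingness reaches about 15%, and is negligible if the base is the per-protocol set.

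The documents do not show that loss will be informative or will differ between arms. They show only that some reasons for removal relate to the co-primary endpoints. The tipping values (about 0.08–0.14 logMAR and 1.8–1.9 h with a 95% interval) are illustrative. Even in a feasibility study the change is worth making, because section 2.3 makes study success depend on both co-primary hypotheses and 14.2 says the data will inform future trials. It is an inexpensive improvement to the analysis and does not invalidate the design.

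**What to change.** In sections 14.3, 14.5, 14.6 and 14.9:

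1. Remove the 15% condition.
2. Always fit the specified primary and secondary models on the ITT set, using all available visits, alongside the per-protocol analysis. State the population for the secondary analysis too. Clarify that the ITT requirement of at least one observation does not remove randomised subjects who lack follow-up data.
3. Add a delta-adjusted analysis. Impute missing values under MAR, then worsen the imputed Test values by delta (higher logMAR, fewer hours, lower CLUE score). Increase delta until non-inferiority is lost and report that value. Do not cap delta at the margin: in the illustration above, a grid ending at 0.05 logMAR or 1 hour would stop before the tipping point and could reassure falsely.
4. Limit the no-imputation sentence in 14.9 to the main analyses, so that it does not conflict with step 3.
5. Report discontinuation reasons by arm beside these results.

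Subjects lost at the Visit 1 fitting have no follow-up outcome, so refitting the model recovers nothing for them. They contribute only through the delta-adjusted imputation.

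The cost is revised wording and modest programming, with no extra subjects, visits or measurements. The drawback is that results may look less clean if the per-protocol and ITT estimates differ or the tipping delta is small.

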14.10. Procedure for Reporting Deviations from Statistical Plan

The analysis will be conducted according to that specified in above sections. There are no known reasons for which it is planned to deviate from these analysis methods. If for any reason a change is made, the change will be documented in the study report along with a justification for the change.

15. DATA HANDLING AND RECORD KEEPING/ARCHIVING

15.1. Electronic Case Report Form/Data Collection

The data for this study will be captured on electronic case report forms (eCRFs) using the BioClinica EDC system. An authorized data originator will enter study data into the eCRFs using the EDC system. Data collected on equipment that is not captured in EDC will be formatted to the specification of the JJVC database manager and sent to JJVC for analysis.

External data sources for this study include: Not Applicable

The clinical data will be recorded on dedicated eCRFs specifically designed to match the study procedures for each visit. Only specifically delegated staff can enter data on a CRF. Once completed, the eCRFs will be reviewed for accuracy and completeness and signed by the Investigator. The sponsor or sponsor's representatives will be authorized to gain access to the subject recordation for the purposes of monitoring and auditing the study.

Edit checks, electronic queries, and audit trails are built into the system to ensure accurate and complete data collection. Data will be transmitted from the clinical site to a secure central database as forms are completed or updated, ensuring information accuracy, security, and confidentiality. After the final database lock, the Investigator will be provided with Individual Patient Profiles (IPP) including the full audit trail on electronic media in PDF format for all of the study data. The IPP must be retained in the study files as a certified copy of the source data for the study.

The content and structure of the eCRFs are compliant with ISO14155:2020.¹

Clinical Study Protocol

Johnson & Johnson Vision Care, Inc.

15.2. Subject Record

At a minimum, subject record should be available for the following:

- subject identification
- eligibility
- study identification
- study discussion
- provision of and date of informed consent
- visit dates
- results of safety and efficacy parameters as required by the protocol
- a record of all adverse events
- follow-up of adverse events
- medical history and concomitant medication
- test article receipt/dispensing/return records
- date of study completion
- reason for early discontinuation of test article or withdrawal from the study, if applicable

The subject record is the eCRF or an external record. The author of an entry in the subject record must be identifiable. The first point of entry is considered to be the source record.

Adverse event notes must be reviewed and initialed by the Investigator.

15.3. Trial Registration on ClinicalTrials.gov

This study will be registered on ClinicalTrials.gov by the Sponsor.

16. DATA MANAGEMENT

16.1. Access to Source Data/Document

The Investigator/Institution will permit trial-related monitoring, audits, IEC/IRB review and regulatory inspection(s) by providing direct access to source data/documents. Should the clinical site be contacted for an audit by an IEC/IRB or regulatory authority, JJVC must be contacted and notified in writing within 24 hours.

16.2. Confidentiality of Information

Information concerning the investigational product and patent application processes, scientific data or other pertinent information is confidential and remains the property of JJVC. The Investigator may use this information for the purposes of the study only. It is understood by the Investigator that JJVC will use information developed in this clinical study in connection with the development of the investigational product and therefore may disclose it as required to other clinical investigators and to regulatory agencies. In order to allow the use of the

Clinical Study Protocol

Johnson & Johnson Vision Care, Inc.

information derived from this clinical study, the Investigator understands that he/she has an obligation to provide complete test results and all data developed during this study to the Sponsor.

